## 5. STUDY OBJECTIVES

The primary, secondary, and exploratory objectives of this study are presented in [Table 5-1](#).

**Table 5-1 G1T28-02: Study Objectives**

	Phase 1b Dose-Finding Portion of Part 1	Phase 2a Expansion Portion of Part 1	Phase 2a Part 2
Primary Objectives			
Assess the DLTs and define the Phase 2 dose of G1T28 administered with E/P therapy	X		
Assess the safety and tolerability of G1T28 administered with E/P therapy	X	X	X
Secondary Objectives			
Assess the PK profile of G1T28	X		
Assess the PK profile of etoposide and carboplatin when administered with G1T28	X		
Assess the hematologic profile (kinetics and incidence/duration/frequency of toxicities) of G1T28 administered with E/P therapy	X	X	X
Assess the incidence of febrile neutropenia	X	X	X
Assess the incidence of infections	X	X	X
Assess the utilization of RBC and platelet transfusions	X	X	X
Assess the utilization of hematopoietic growth factors	X	X	X
Assess the utilization of systemic antibiotics	X	X	X
Assess the incidence of chemotherapy dose reductions and dose interruptions overall	X	X	X
Assess the incidence of Grade 2 or greater nephrotoxicity	X	X	X
Assess tumor response based on RECIST, Version 1.1	X	X	X
Assess PFS and overall survival	X	X	X
Exploratory Objectives			
Assess the incidence of mucositis	X	X	X
Assess the incidence of alopecia	X	X	X
Assess the incidence of fatigue	X	X	X
Assess patient-reported QOL	X	X	X
Assess immunologic markers			X

DLT = dose-limiting toxicity; E/P therapy = etoposide + carboplatin on Day 1 and etoposide on Days 2 and 3 of 21-day cycles; PFS = progression-free survival; PK = pharmacokinetic; QOL = quality of life; RBC = red blood cell; RECIST = Response Evaluation Criteria in Solid Tumors

## **6. INVESTIGATIONAL PLAN**

### **6.1. Overall Study Design and Plan**

[figure not shown]
This is a randomized, double-blind, placebo-controlled, multicenter, Phase 1b/2a study of the safety and PK of G1T28 in combination with E/P therapy for patients with newly diagnosed extensive-stage SCLC. The study consists of 2 parts: Part 1 will be a limited Phase 1b, open-label, dose-finding portion followed by a Phase 2a, open-label, expansion portion in up to 18 patients at the selected dose to be used in Part 2. Prior to initiating Part 2, up to a total of 24 patients will be enrolled at the chosen Part 2 dose (6 patients in the dose-finding portion of Part 1 and up to 18 patients in the Phase 2a, open-label, expansion portion of Part 1). Part 2 will consist of a randomized, double-blind cohort (70 patients will be randomly assigned to G1T28 administered IV with E/P therapy or placebo administered IV with E/P therapy). All parts of the study include 3 study phases: Screening Phase, Treatment Phase, and Survival Follow-up Phase. The Treatment Phase begins on the day of first dose with study treatment and completes at the Post-Treatment Visit.

The initial diagnosis of SCLC should be made based on standard pathological examination, preferably including immunohistochemical staining for neuroendocrine features. Archived tumor samples should be available for sending to a central pathology laboratory to confirm the diagnosis of SCLC. If central pathology review does not confirm SCLC diagnosis, the patient may be withdrawn from the study after consultation between the principal investigator, medical monitor, and sponsor. Available tissue after confirming the diagnosis of SCLC will be banked for assessment of relevant DNA, ribonucleic acid (RNA), and protein markers, such as those involved in the CDK4/6 pathway.

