The principal component of this therapeutic approach is to transiently arrest HSPCs in the G1 phase of the cell cycle while chemotherapy is administered. It is imperative that this therapeutic approach provides selective bone marrow protection without antagonizing the tumor efficacy of chemotherapy. To ensure this second feature, patients are required to have CDK4/6-independent tumors. The downstream target of CDK4/6 is the retinoblastoma (Rb) protein, which is phosphorylated upon CDK4/6 activation, allowing the cell to enter into the S phase of the cell cycle (synthesis phase of cell cycle in which DNA is replicated). In order to promote G1 cell cycle arrest by utilizing a CDK4/6 inhibitor, a functional Rb protein is required. For SCLC, historical reports have consistently shown the most prevalent inactivated tumor suppressor genes are tumor protein 53 (TP53) and retinoblastoma 1 (RB-1) (D'Amico 1992; Heighway 2004; Yuan 1999; Cagle 1997; Gouyer 1994), and it has been accepted that almost all cases of SCLC are functionally Rb null. In addition, 2 recent reports provided a detailed characterization of the genomic landscape of SCLC using next generation sequencing approaches, including full exome sequencing, transcriptome profiling by RNA sequencing (RNASeq), copy number analyses, and limited whole genome sequencing to identify translocations (Peifer 2012; Rudin 2012). These reports confirmed what had been previously proposed in studies that examined a smaller number of tumors, namely that concomitant inactivation of TP53 and RB-1 are driver mutations and occur nearly universally in SCLC. Consistent with these data, preclinical in vitro and in vivo studies have demonstrated that G1T28 exposure prior to chemotherapy does not diminish the effect of

chemotherapy in tumors that are RB-1 inactive, including SCLC. Therefore, as a result of near universal RB-1 inactivation, SCLC is inherently CDK4/6-independent, which should allow selective protection of the HSPCs but not the tumor from the effects of chemotherapy.

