#### **4.5. Risk/Benefit Assessment**

G1T28 is being developed to reduce chemotherapy-induced myelosuppression, which is a significant issue. Bone marrow HSPCs require CDK4/6 for proliferation. SCLC tumors are almost universally CDK4/6 independent by virtue of various genetic mutations in the RB-1 gene that result in the loss of the Rb protein, which is the downstream target of CDK4/6. Therefore, the risk of producing a G1 cell cycle arrest of the tumor cells, and thereby protecting the tumor from chemotherapy, is small. As stated in Section 4.4, the BED of IV G1T28 is 192 mg/m^2 and a dose of 200 mg/m^2 will be used as the starting dose for administration on Days 1 to 3 of every 21-day cycle of E/P therapy in the present study. In conclusion, the potential benefits of combining G1T28 at a dose of 200 mg/m^2 with E/P therapy to protect the bone marrow HSPCs outweigh the potential risks.

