#### **11.4. Central Pathology Review to Confirm Diagnosis of SCLC**

Archived tumor samples should be sent to the central pathology laboratory as soon as possible after enrollment to confirm the diagnosis of SCLC. Available tissue after confirming the diagnosis of SCLC will be banked for assessment of relevant DNA, RNA, and protein markers, such as those involved in the CDK4/6 pathway (as described in the Laboratory Manual). If central pathology review does not confirm SCLC diagnosis, the patient may be withdrawn from the study after consultation between the principal investigator, medical monitor, and sponsor. Archived tumor samples may also be used for future genomic testing related to the mechanism of drug action.

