### **12.3. Discontinuation of Study Drug**

Study drug will be discontinued if any of the following events occur during the study:

- A patient suffers an AE that, in the judgment of the investigator, sponsor, or medical monitor, presents an unacceptable risk to the patient
- General or specific changes in the patient's condition (eg, a significant intercurrent illness or complication) that, in the judgment of the investigator, are unacceptable for further administration of study drug
- Occurrence of pregnancy
- Significant noncompliance with protocol requirements
- The sponsor or legal representative of the sponsor requests the patient to withdraw
- Patient has radiologically documented disease progression

In the event of study drug discontinuation, patients should be strongly encouraged to complete all scheduled assessments through the end of their current 21-day treatment cycle, including the PRO scales; CBC assessment on Day 22; the Post-Treatment Visit; and the Survival Follow-up Phase of the study. A patient who discontinues study treatment for reasons other than PD will have a CT or MRI scan at the Post-Treatment Visit, if they have not had a scan within the prior 4 weeks.

The investigator will document the reason for study drug discontinuation on the applicable eCRF page.

When discontinuation is due to a SAE or a Grade 3 or 4 toxicity considered to be related to study medication, the investigator should follow the event until resolution, return to baseline,

or it is deemed that further recovery is unlikely. Data on these events should be collected on the AE CRF.

In the event a patient discontinues due to an AE or pregnancy, the investigator should notify the medical monitor by telephone within 48 hours of study drug discontinuation.

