#### **12.4. Withdrawal of Patients from the Study**

Patients may withdraw from the study at their own discretion (or at the discretion of the investigator) for any reason at any time. The following list of reasons for withdrawing patients from the study may include but are not limited to:

- Withdrawal of informed consent
- Lost to follow-up (must have at least 2 documented attempts to contact the patient; 1 attempt must be written to the patient and sent via certified letter)
- If central pathology review does not confirm SCLC diagnosis, the patient may be withdrawn from the study after consultation between the principal investigator, medical monitor, and sponsor

All data collected prior to the date of withdrawal of consent will remain in the clinical database.

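### A patient whose SCLC is not centrally confirmed may be withdrawn from the whole study, so survival follow-up can end early in someone who stays in the FAS

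*Protocol*

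**What the plan says.** Protocol Section 11.4 sets the timing: "Archived tumor samples should be sent to the central pathology laboratory as soon as possible after enrollment to confirm the diagnosis of SCLC". In Part 2, randomization falls within the 3 days before the first dose (Section 10.2), so the central result arrives after randomization. No section makes dosing wait for the result or gives a deadline for it.

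The consequence is in Section 6.1: "If central pathology review does not confirm SCLC diagnosis, the patient may be withdrawn from the study". The decision is taken in consultation between the principal investigator, the medical monitor and the sponsor, and no criteria are given. The rule is repeated in Sections 10.2 and 11.4, in Table 9-1 footnote n and in SAP Table 2 footnote n.

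Section 12.4, on leaving the study, lists this reason beside withdrawn consent and loss to follow-up under the words "The following list of reasons for withdrawing patients from the study may include but are not limited to". It is absent from the list in Section 12.3, on stopping study drug, which adds: "In the event of study drug discontinuation, patients should be strongly encouraged to complete all scheduled assessments". That encouragement extends to the Post-Treatment Visit and the Survival Follow-up Phase. Section 12.4 has nothing comparable.

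On why the diagnosis matters, Section 4.1 says of avoiding antagonism of chemotherapy: "To ensure this second feature, patients are required to have CDK4/6-independent tumors". Section 4.5 concludes: "Therefore, the risk of producing a G1 cell cycle arrest of the tumor cells, and thereby protecting the tumor from chemotherapy, is small". Its ground is the near-universal loss of Rb in SCLC.

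In the SAP, dosed randomized patients remain in the FAS by assigned arm whatever their protocol deviations (Sections 3.1.1 and 3.2). OS is censored at the date last known alive (Section 5.2.8).

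**The concern.** Tumor response, PFS and OS are listed among the safety endpoints (Protocol Section 13.5.1). They are where protection of the tumor from chemotherapy would show. The argument that such protection is unlikely depends on the tumor being SCLC. A patient whose SCLC is not confirmed is therefore one to whom the argument may not apply, and the protocol permits follow-up to end in just that patient.

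In the analysis, the patient is kept in the FAS denominator but contributes survival time only up to about the date of withdrawal. That is censoring by decision, after randomization, for a reason tied to tumor type, so it may be informative. It is also avoidable, because the protocol already has a route (Section 12.3) that handles study drug separately from follow-up.

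**Working it through.** **1. The two routes side by side**

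| | Study drug stopped (Section 12.3) | Withdrawn from study (Section 12.4) |
|---|---|---|
| Central non-confirmation listed | No | Yes |
| Post-Treatment Visit and survival follow-up | Strongly encouraged | Not mentioned |
| Scans every 2 months if not progressed | Yes (Section 10.7) | Not mentioned |
| FAS membership, Part 2 (SAP 3.1.1, 3.2) | Kept if dosed | Kept if dosed |
| OS (SAP 5.2.8) | Followed to death or last contact | Censored at date last known alive |

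The only statement in Section 12.4 about data concerns data collected before consent is withdrawn, which is a different event.

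**2. PFS is a separate problem.** SAP Table 18 has a row that censors PFS at the last progression-free assessment when treatment stops for a reason other than progression. Protocol Section 10.7 continues scans in those same patients. A patient who stops drug and later progresses on a scan fits both that row and the disease-progression row, and the table does not say which governs. Changing the route from 12.4 to 12.3 therefore secures OS but not PFS.

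**3. The plan's own figures.** No stated figure depends on this rule. The only sample-size figures are the precision statements for 35 per arm, and both reproduce:
- Wilson half-width at p = 0.5: z/(1 + z²/n) × √(p(1−p)/n + z²/(4n²)), with z = 1.96 and n = 35, gives 0.157 (stated 0.157).
- t half-width: t(0.975, 34)/√35 = 0.3435 SD (stated 0.344 SD).

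**4. Number of patients.** The non-confirmation rate q is an assumption, taken as 3-5%, with all such patients withdrawn. With 70 randomized, 0.03 × 70 = 2.1 and 0.05 × 70 = 3.5, so about 2-4 patients. With 1:1 allocation about half are on placebo, leaving roughly 1-2 on G1T28.

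**5. Deaths.** Survival follow-up runs at least until 50% of Part 2 patients have died (35 of 70). SAP Section 6.2.12 gives about 55 deaths for the end-of-study analysis. (It equates this with about 70% maturity, but 0.70 × 70 = 49, so the range 35 to 55 is used.) If deaths are proportional to patients:
- at 35 deaths: 0.03 × 35 = 1.05 to 0.05 × 35 = 1.75 lost;
- at 55 deaths: 0.03 × 55 = 1.65 to 0.05 × 55 = 2.75 lost.

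In both cases this is 3-5% of deaths.

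**6. Effect on the OS hazard ratio.** With 1:1 allocation, SE(log HR) ≈ 2/√deaths. This is 0.338 at 35 deaths and 0.270 at 55, or 0.347 and 0.277 after a 5% loss. The corresponding 95% CI factors without loss, exp(1.96 × SE), are 1.94 and 1.70.

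Suppose the true HR is 1.0 in confirmed patients and h in non-confirmed patients. Approximating the pooled log HR as the death-weighted mean, the pooled HR with everyone retained is exp(q × ln h):

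| q | h = 1.5 | h = 2 | h = 3 |
|---|---|---|---|
| 3% | 1.01 | 1.02 | 1.03 |
| 5% | 1.02 | 1.04 | 1.06 |
| 10% | 1.04 | 1.07 | 1.12 |

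If they are dropped it is 1.00. The shift is small against a CI factor of 1.7 to 1.9.

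**The case against.** Much can be said for the plan, and several stronger readings do not survive.

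- **That follow-up is lost.** A reader might infer this, but withdrawal is permissive and follows consultation. Section 11.3.1.10 also asks investigators to report later deaths or adverse events that may be related to study drug. That is only partial cover: it depends on a causality judgment and does not collect survival status.
- **That removal could favor one arm.** The trigger is archived, pre-treatment tissue sent as soon as possible. In Part 2 the investigators, and the sponsor staff or designees conducting the study, are blinded (Section 8.5). Selection that knowingly depends on arm is not supported. Blinding does not exclude a decision influenced by clinical course, since no deadline or criteria are set.
- **That non-confirmed means not SCLC.** Eligibility already requires an unequivocal local diagnosis, so non-confirmation could reflect limited material. The documents give no Rb status for these patients, and tissue banking for such markers is described only once SCLC is confirmed: "Available tissue after confirming the diagnosis of SCLC will be banked for assessment of relevant DNA". That tumor protection is more plausible in them is an inference from the protocol's rationale.
- **That 4-7% of deaths are at stake.** Dividing 2 to 4 patients by 55 deaths gives 3.6% to 7.3%, but this sets patients against deaths and requires every one of them to die. The proportional figure is 3-5%.
- **That the wording is only loose.** Section 6.1.3 also speaks of discontinuation from the study where Section 8.4.4.2 speaks of discontinuing chemotherapy. Perhaps only study drug was meant here too. If so, the text still needs correcting, because Section 12.4 lists this reason explicitly as study withdrawal.
- **That the SAP already covers it.** FAS inclusion is indeed stated, and a per-protocol set exists, but central pathology status is not named in its criteria or in the subgroup list (SAP Section 6.2.9).

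Patients may also leave of their own accord, so continued follow-up cannot be guaranteed, and Section 12.3 itself only encourages it.

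**Conclusion.** The point holds as a limited one. Both documents allow a discretionary withdrawal from the study, after randomization in Part 2, when central review does not confirm SCLC, and neither provides for survival calls or scans afterwards. The result is possible early censoring for OS in a patient who remains in the FAS and whom the CDK4/6-independence argument may not cover.

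The size is unknown. On an assumed 3-5% non-confirmation, with all such patients withdrawn and deaths in proportion, it is about 2-4 of 70 patients and 3-5% of deaths. The pooled HR would move by a few hundredths at most. The case rests on which patients are affected, not on precision or power. The documents do not support a claim that follow-up is routinely lost, that the comparison is biased by arm, or that harm would be hidden. It is a cheap improvement, not a threat to the study's conclusions.

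**What to change.** 1. In Protocol Sections 6.1, 10.2, 11.4 and 12.4, Table 9-1 footnote n and SAP Table 2 footnote n, separate the two consequences of central non-confirmation. Any decision on study drug stays with the existing consultation and falls under Section 12.3. Non-confirmation is no longer in itself a reason for study withdrawal under Section 12.4.
2. State in the same places that, unless consent is withdrawn, survival follow-up and scheduled tumor assessments continue, and that a dosed Part 2 patient is analysed in the FAS by assigned arm.
3. Reconcile the SAP Table 18 row on treatment discontinuation for reasons other than progression with the continued scans in Protocol Section 10.7, and say which row governs when progression is documented later. Without this only OS benefits. The separate row for new anticancer treatment would still censor PFS.
4. Add one sensitivity analysis of ORR, PFS and OS excluding centrally non-confirmed patients.

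The cost is protocol and SAP wording, a few extra monthly calls and scans for perhaps two to four patients, and one extra analysis run. The planned number of patients and the precision statements do not change.

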#### **6.1.1. Part 1**

The goal of the Phase 1b dose-finding portion of Part 1 is to assess the safety, including DLTs (see Section 6.1.1.1), and PK (see Section 6.1.1.2) of G1T28 administered at a starting dose of 200 mg/m^2 (derived from Study G1T28-1-01, a Phase 1a, safety, PK, and pharmacodynamic study of G1T28 in healthy male and female patients) once daily on Days 1 to 3 of E/P therapy (Figure 6-1).

**Figure 6-1 Study Schema: Phase 1b Dose-Finding Portion of Part 1**

E/P = etoposide + carboplatin

- a Safety and available PK data from Cycle 1 will be considered in making dose escalation/de-escalation decisions (if required) and enrolling additional cohorts
- b G1T28 + E/P will continue until disease progression, unacceptable toxicity, or discontinuation by the patient or investigator (eg, after completing 6 cycles). The tumor should be assessed after every even cycle using Response Evaluation Criteria in Solid Tumors (RECIST), Version 1.1. Assessments should be performed within 7 days of starting the subsequent cycle.
- c G1T28 will be administered prior to the administration of etoposide and carboplatin on Day 1 and administration of etoposide on Days 2 and 3 of 21-day cycles
- d Patients will return to the study center for a Post-Treatment Visit at 30 + 3 days after the last dose of study drug.
- e The Survival Follow-up Phase will continue until at least 50% of the patients randomized to Part 2 of the study have died.

#### 6.1.1.1. Definition of Dose-Limiting Toxicities (Applicable to Cycle 1 of the Phase 1b Dose-Finding Portion of Part 1)

Dose-limiting toxicities are drug-related toxicities defined as follows:

- Absolute neutrophil count (ANC)  $< 0.5 \times 10^9/L$  lasting for  $\geq 7$  days
- $\geq$  Grade 3 neutropenic infection/febrile neutropenia
- Grade 4 thrombocytopenia or  $\geq$  Grade 3 thrombocytopenia with bleeding
- Unable to start next cycle of chemotherapy due to lack of recovery to an ANC  $\geq 1.5 \times 10^9/L$  and platelet count  $\geq 100 \times 10^9/L$
- $\geq$  Grade 3 nonhematologic toxicity (nausea, vomiting, and diarrhea failing maximal medical management; fatigue lasting for  $> 72$  hours)

Toxicities not clearly related to etoposide/carboplatin (E/P) therapy will also be considered for the purposes of determining DLTs.

#### 6.1.1.2. Criteria for Adjusting G1T28 Dose Based on Pharmacokinetic Parameters

The PK profile of G1T28 is well established in healthy subjects, with good estimates of key parameters such as  $C_{max}$ , AUC, and CL. In addition, the intersubject variability in these PK parameters is low (see Section 4.2). However, patients with SCLC enrolled in this study will likely be older and have more comorbidities compared with subjects enrolled in the Phase 1a G1T28-1-01 study, and therefore, could demonstrate differences in PK.

Based on the observed PK profile of G1T28 in Study G1T28-1-01, the extrapolated  $AUC_{0-24.5h}$  for a 200 mg/m^2 dose is 3100 h•ng/mL. If the mean  $AUC_{0-24.5h}$  in the initial cohort of patients (6 patients) in the Phase 1b, dose-finding portion of Part 1 is not within 20% of the target (eg, 2480 to 3720 h•ng/mL), then the dose of G1T28 will be adjusted in the next cohort of 6 patients to achieve a mean  $AUC_{0-24.5h}$  of 3100 h•ng/mL. The magnitude of the dose modification is based upon the fact that G1T28 displays linear PK over the dose range studied to date. Any available PK data from additional cohort(s) of the Phase 1b dose-finding portion of Part 1 may be utilized for modifying the G1T28 dose (if required). If the G1T28 dose level for a subsequent cohort requires escalation, the increase will not exceed 30% from the previous dose level. A G1 cell cycle arrest of a minimum of 24 hours after G1T28 administration is desired to ensure that the bone marrow arrest is maintained long enough to avoid releasing HSPCs into the S (DNA synthesis) phase of the cell cycle in the presence of high concentrations of chemotherapy and thereby potentially exacerbating myelosuppression.

If the dose is adjusted due to DLTs and the PK was within the expected target range, then a new target  $AUC_{0-24.5h}$  will be calculated for the modified dose as follows:

$$Y = 2.11 + 1.1 * X, \text{ where } Y \text{ is the } \ln(AUC_{0-24.5}) \text{ h} \cdot \text{ng/mL} \text{ and } X \text{ is the } \ln(\text{dose}) \text{ mg/m}^2$$

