**Part 1**

The goal of the Phase 1b dose-finding portion of Part 1 is to assess the safety, including dose-limiting toxicities (DLTs), and PK of G1T28 administered at a starting dose of 200 mg/m^2 (derived from Study G1T28-1-01, a Phase 1a, safety, PK, and pharmacodynamic study of G1T28 in healthy male and female patients) on Days 1 to 3 of E/P therapy.

The goal of the Phase 2a expansion cohort of Part 1 is to obtain additional safety and efficacy data for G1T28 in combination with E/P to inform further development in newly diagnosed extensive-stage SCLC.

Six patients will initially be enrolled in the Phase 1b dose-finding portion of Part 1. Depending on the evaluation of DLTs and PK parameters from these initial patients in Cycle 1, additional cohorts of 6 patients may be enrolled at higher or lower doses. The PK profile of G1T28 is well established in healthy subjects, with good estimates of key parameters such as maximum concentration (Cmax), area under the concentration-time curve (AUC), and Clearance (CL). In addition, the

---

intersubject variability in these PK parameters is low (see Section 4.2). Therefore, for the initial cohort of 6 patients treated with 200 mg/m^2, the target AUC0-24.5h is 3100 h•ng/mL. If the mean AUC0-24.5h is not within 20% of this target (AUC 2480 to 3720 h•ng/mL), the dose of G1T28 will be adjusted in the next cohort of 6 patients to achieve a mean AUC0-24.5h of 3100 h•ng/mL. Any available PK data from additional cohort(s) of the Phase 1b dose finding portion of Part 1 may be utilized for modifying the G1T28 dose (if required). If the G1T28 dose level for a subsequent cohort requires escalation, the increase will not exceed 30% from the previous dose level. The magnitude of the dose modification is based upon the fact that G1T28 displays linear PK over the dose range studied to date. The adjusted dose, if necessary, will be tested in 6 additional patients enrolled in the Phase 1b dose-finding portion of Part 1, and up to 18 patients will be enrolled at the chosen Part 2 dose in the Phase 2a expansion portion of Part 1, prior to initiating the randomized part (Part 2) of the study.

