Following a single 30-minute IV infusion of G1T28, the median time to reach the maximum concentration (Tmax) ranged between 0.25 and 0.47 hour after the start of infusion. The maximum concentration (Cmax) increased in a dose-proportional manner following a single 30-minute IV infusion of G1T28 over the dose range of 6 to 192 mg/m^2. Total systemic (area under the concentration-time curve [AUC]) exposure increased more than dose proportionally over the dose range of 6 to 192 mg/m^2 of G1T28. The elimination kinetics of G1T28 appeared to follow a 3-compartment model. The geometric mean half-life (t1/2) was 12.9 to 14.7 hours for the 48 to 192 mg/m^2 dose levels. The interpatient variability (%CV) of the PK parameters at the 192 mg/m^2 dose level was low (<15%). The PK of G1T28 suggests that drug accumulation following repeated administration is unlikely to occur. Urinary excretion appears to be a minor route of elimination for unchanged G1T28.

G1T28 showed positive pharmacodynamic effects in 2 assays. Dose-dependent inhibition of ex vivo whole blood stimulation occurred following a single IV infusion of G1T28 at 96 and 192 mg/m^2 (maximum mean inhibition of 37.2% and 60%, respectively, occurred 4 hours

after the end of infusion). Lymphocyte proliferation started to recover 8 hours after the end of infusion, but inhibition of proliferation persisted until the last sampling time point of 24 hours. Assessment of bone marrow 24 hours after administration of G1T28 at the biologically effective dose (BED) of 192 mg/m^2 revealed a significant decrease in the number of HSPCs in the synthesis (S)/gap 2 (G2)/mitosis (M) phases of the cell cycle (ie, an increase in the proportion of cells in G1 arrest). This G1 arrest persisted in the different progenitor lineages 32 hours after dosing. However, no changes were noted in the peripheral blood counts, indicating that the bone marrow arrest is transient and reversible and is consistent with the effects seen in animals.

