- If there is > 1 DLT in the first cohort of 6 patients enrolled in the Phase 1b dose-finding portion of Part 1 and the available G1T28 PK parameters from these 6 patients are as predicted (Section 6.1.1.2), the dose of G1T28 should be decreased to 160 mg/m^2 and an additional 6 patients should be enrolled at the modified G1T28 dose in combination with E/P therapy. For assessment of data from the second cohort enrolled in the Phase 1b dose-finding portion of Part 1, please see the decision tree in [Figure 6-2](#).
- If there is > 1 DLT following a G1T28 dose of 160 mg/m^2 in combination with E/P therapy in the second cohort of patients and if available, PK parameters are as predicted (Section 6.1.1.2), an additional cohort of 6 patients will be enrolled at a further decreased G1T28 dose of 130 mg/m^2 in combination with E/P therapy. For assessment of data from the third cohort enrolled in the Phase 1b dose-finding portion of Part 1, please see the decision tree in [Figure 6-2](#).
- If there is > 1 DLT following the second dose reduction of G1T28 and if available, PK parameters from the third cohort are as predicted (Section 6.1.1.2), no further dose modifications will be made and the study will be terminated.
- At any time, if ≥ 2 DLTs are observed in any given cohort, further enrollment into that cohort will be stopped until the SMC can review the available data and make dose and cohort recommendations.

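### The formula for a DLT-reduced G1T28 dose returns 2802 h•ng/mL at 200 mg/m², not the stated 3100, so the AUC targets at 160 and 130 mg/m² sit 9.6% below values consistent with 3100

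*Protocol*

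**What the plan says.** Protocol Section 6.1.1.2 sets the exposure benchmark for the dose-finding portion. The AUC0-24.5h extrapolated from the Phase 1a study "for a 200 mg/m 2 dose is 3100 h•ng/mL". The dose is adjusted if the first-cohort mean "is not within 20% of the target (eg, 2480 to 3720 h•ng/mL").

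A second rule in the same section covers dose changes made for toxicity while first-cohort PK was in range. For that case the protocol directs: "then a new target $AUC_{0-24.5h}$ will be calculated for the modified dose as follows". The equation printed there is Y = 2.11 + 1.1 X, with Y the natural log of AUC0-24.5h and X the natural log of the dose in mg/m².

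Section 6.1.1.3 uses the benchmark as a branch condition. With more than one DLT at 200 mg/m² and PK as predicted, "the dose of G1T28 should be decreased to 160 mg/m 2". After more than one DLT at 160 mg/m², if "PK parameters are as predicted (Section 6.1.1.2), an additional cohort of 6 patients will be enrolled at a further decreased G1T28 dose", that next dose is 130 mg/m². More than one DLT there, again with PK as predicted, ends the study.

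The protocol does not say how 3100 was extrapolated, how the coefficients were fitted or rounded, or why the two differ.

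**The concern.** Both figures describe the same quantity, expected AUC0-24.5h at a given dose, and both serve as targets in one decision scheme. They should agree at 200 mg/m², and they do not. A switch from the stated target to the formula therefore lowers the benchmark for two reasons at once: the dose is lower, as intended, and the calibration is about 10% lower, which nothing in the text explains. A cohort whose exposure simply follows from an acceptable first cohort could then be judged too high. The benchmark feeds the dose recommendation, so the two figures should share one calibration.

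**Working it through.** **Inputs.** Target 3100 at 200 mg/m², ±20% window, and formula: Protocol 6.1.1.2. Reduced doses 160 and 130 mg/m², cohorts of 6: Protocol 6.1.1.3. Between-subject CV below 15% at 192 mg/m² in healthy subjects: Protocol 4.2. AUC in h•ng/mL.

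**Step 1: the plan's own window.** 0.8 × 3100 = 2480 and 1.2 × 3100 = 3720. Reproduced.

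**Step 2: the formula at 200 mg/m².** ln 200 = 5.2983; 2.11 + 1.1 × 5.2983 = 7.9382; exp(7.9382) = 2802. Ratio 2802/3100 = 0.904, or 9.6% low. The stated 3100 is not reproduced. The formula reaches 3100 only at about 219 mg/m².

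**Step 3: reduced doses.** The consistent target is 3100 × (dose/200)^1.1.

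| Dose | Printed formula (±20%) | Consistent with 3100 (±20%) |
|---|---|---|
| 160 | 2192 (1754 to 2631) | 2425 (1940 to 2910) |
| 130 | 1745 (1396 to 2094) | 1930 (1544 to 2316) |

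Both use slope 1.1, so the ratio is 0.904 at every dose.

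**Step 4: can rounding explain it?** Intercept 2.105 to 2.115 gives 2788 to 2816 at 200 mg/m². Adding slope 1.095 to 1.105 gives 2715 to 2892. Only if 1.1 is a one-decimal rounding (1.05 to 1.15) is 3100 covered, and the range is then 2139 to 3670, wider than the acceptance window itself. With slope 1.1, the intercept that gives 3100 is ln 3100 − 1.1 ln 200 = 8.0392 − 5.8282 = 2.211. With intercept 2.11, the slope is (8.0392 − 2.11)/5.2983 = 1.119.

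**Step 5: conflict without any variability assumption.** Take the ±20% window as carried over. The upper limit at 160 mg/m² is 2631. In 200 mg/m² terms this is 2631/0.8^1.1 = 2631/0.7824 = 3363. A first-cohort mean between 3363 and 3720 is in range at 200 mg/m²; with unchanged PK it becomes 2631 to 2910 at 160 mg/m², above the printed window.

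**Step 6: with sampling variation.** Let the true mean at 160 mg/m² be 2425, n = 6, with a normal cohort mean and SE = CV × mean/√6. At CV 15%, the SE is 6.12% of the mean. The printed limits are 1.0847 and 0.7231 times the true mean, so z = 0.0847/0.0612 = 1.38 above and −4.5 below, and P(off target) = 8.3%. With the consistent target, z = ±0.20/0.0612 = ±3.27 and P = 0.1%. The other CVs are assumptions; patients may vary more than healthy subjects.

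| CV | Printed formula | Consistent target |
|---|---|---|
| 10% | 1.9% | 0.0% |
| 15% | 8.3% | 0.1% |
| 20% | 15.0% | 1.4% |
| 25% | 20.7% | 5.0% |
| 30% | 25.6% | 10.2% |

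**Step 7: the opposite case.** If the formula is right and 3100 is wrong, the true mean at 200 mg/m² is 2802. The first cohort would then be called off target 3.0% of the time at CV 15% and 17.8% at CV 30%, against 0.1% and 10.2% with a consistent target.

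**The case against.** The case on the other side is substantial.

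- **Reach.** The formula is used only after a DLT-driven change with PK in range; a PK-driven change keeps the 3100 target. PK sampling after Cohort 1 is optional (Section 11.2; Table 9-1, footnote o). The criteria guide decisions, but the SMC is responsible for them (Sections 6.1.1.3 and 6.1.1.4). This stands, and the percentages above are conditional on all of it.
- **Window.** ±20% is stated only for the first cohort. For later cohorts it is implied by the references back to Section 6.1.1.2. This also stands as an assumption.
- **Two estimators.** A log-log line fitted over 6 to 192 mg/m² need not pass through a value extrapolated from near the top dose. A reader might infer a proven misprint, but the documents do not establish one. They do show two targets on different calibrations.
- **Low exposure.** A reader might infer that exposure too low at 200 mg/m² could be accepted at 160 mg/m². With unchanged PK it cannot: a first-cohort mean of 2242 to 2480 is already out of range, so the formula is not invoked and the next cohort is dosed towards 3100.
- **Consequence.** Later-cohort decisions are referred to Figure 6-2, which is not reproduced in the text reviewed. After more than one DLT at 160 mg/m², PK as predicted already leads to 130 mg/m², and PK judged too high would also point downwards. A changed final action is therefore not shown.
- **Actual use.** SAP Section 5.1.3.3 (footnote to Table 9) lists only 200 and 240 mg/m² in Part 1, so the reduced-dose branch appears unused. That limits the practical harm; it does not reconcile the figures.

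Two neighbouring points are too small to press. The Synopsis says "G1T28 displays linear PK over the dose range studied to date", while Section 4.2 says AUC "exposure increased more than dose proportionally over the dose range of 6 to 192 mg/m 2 of G1T28". Linear scaling gives 3100 × 0.8 = 2480 at 160 mg/m² against 2425, a difference of about 2%; over the maximum 30% escalation it is 1.3^0.1 = 1.027. Arithmetic and geometric means differ by about 1.1% at CV 15%. Both are minor against ±20%.

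**Conclusion.** The inconsistency is real and can be checked from one section: the printed formula and the stated target differ by 9.6% at 200 mg/m², and every target from the formula carries that gap. Its effect is confined to cohort means near the window edges. With exposure on the 3100-consistent target at 160 mg/m², a cohort still passes about 92% of the time at CV 15%. The off-target rate of about 8% rests on 3100 being the right anchor, the ±20% window carrying over, six patients, normally distributed means and the assumed CV.

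A reader might infer that the PK rule gives wrong verdicts in general, or that the Part 2 dose was affected. The documents support neither: the formula has a narrow trigger, its branch appears unused, and nothing shows whether 3100 or the formula is correct. The supportable conclusion is that the two benchmarks conflict and could give inconsistent verdicts near the upper edge of the window after a DLT-driven reduction.

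**What to change.** Check the Phase 1a regression output and make the two figures agree at 200 mg/m², in one of these ways:

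- Correct the coefficients and print them to three decimals. With slope 1.1, an intercept of about 2.21 reproduces 3100.
- Define the reduced-dose target as 3100 × (dose/200)^b, with b the fitted exponent.
- If the formula proves right, correct 3100 and its 2480 to 3720 window instead, in Section 6.1.1.2 and the Synopsis.

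The sponsor must take the choice from its own fit. In the same edit, state that the ±20% window applies to the new targets, if that is intended. The cost is one regression recheck and a few lines of protocol text, with no extra patients, samples or visits.
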